# 4.4 Exclusion Criteria, Step 2: Continuation for Cohort 1 and Cohort 2a to injection phase

Participants in Cohort 1 or Cohort 2a who meet any of the following criteria will be excluded from Step 2:

- **4.4.1** Has permanently discontinued oral study product.
- **4.4.2** Occurrence of any grade 3 or higher adverse event assessed as related to study product during Step 1.
- **4.4.3** Any other condition or social circumstance situation that, in the opinion of the IoR or designee, would make continued study participation unsafe, complicate interpretation of study outcome data, or otherwise interfere with achieving the study objectives.

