## 6.3.3 Week 4a Visit: Step 1 – oral phase for Cohort 1 and Cohort 2a

Participants and their parents/guardians should be reminded to return all oral study product at the Week 4a visit, for the adherence assessment, and to hold administration of the oral product for observed dosing at the clinic. Additional oral study product may be dispensed at this visit if needed to provide coverage until the Week 4b visit.

Data collected through the Week 4a study visit will be assessed to determine eligibility to enter Step 2 and receive injectable CAB LA + RPV LA. Week 4a visit laboratory test results should be reviewed as soon as they are available, for determining Step 2 eligibility and scheduling the Week 4b visit. Abnormal laboratory test result values from the Week 4a visit may be repeated prior to scheduling the Week 4b visit. If laboratory test results confirm Step 2 eligibility, and all other eligibility criteria are met, the Week 4b visit may be scheduled within the target visit window for Step 2 Entry and injectable study product administration, and may be combined with the Week 4a visit. See Section 4.3 and Section 4.4 for Step 2 eligibility criteria.

If participants are ineligible to receive injectable study product in Step 2, they will permanently discontinue oral study product use and complete an Early Termination visit 28 days after their last oral study product dose (see Section 6.6.2).

Cohort 1 an	nd Cohort 2	2a Week 4a Visit Procedures (Step 1 – oral phase)
Behavioral a	nd	Provide adherence counseling
Counseling		Provide contraceptive counseling^
Clinical		Update medical and medications history
(prior to disp		Perform complete physical exam
oral study pr	roduct)	Perform adherence assessment
		Identify/review/update adverse events
Laboratory	Blood	Collect blood for:
		
 
Hematology: CBC (WBC, RBC, hemoglobin, hematocrit, MCV, MCHC) with differential, ANC (absolute neutrophil count), and platelet count
 
Chemistries: Creatinine, eGFR, CK, Direct bilirubin, Total bilirubin, BUN, AST, ALT, Lipase, Albumin
 

	Blood or Urine	Pregnancy test, prior to dispensing oral study product^
Study product		Prescribe and dispense oral study product, if indicated
		Facilitate administration of oral study products (including provision of a meal)

^ For participants of childbearing potential.

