#### Adverse Events

Adverse events will be entered into the adverse events eCRFs:

- Grade 1 and higher clinical adverse events
- Grade 3 or higher laboratory-only adverse events
- Grade 1 or 2 laboratory adverse events that result in temporary study product hold or permanent discontinuation of study product
- Adverse events that meet criteria for expedited reporting per protocol Section 7.3.2

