# 8.1.1 General Management of Adverse Events

Sections 8.1.2—8.3 provide detailed participant and study product management on specified adverse events including specified abnormal laboratory test result values. If an observed adverse event or abnormal laboratory test result value is not listed in those sections below, the guidance in this section (General Management of Adverse Events) should be followed.

In general, the IoR or designee has the discretion to temporarily hold study product at any time if they feel that continued product use would be harmful to the participant or interfere with treatment deemed clinically necessary. See Sections 8.4 and 8.5 below.

- Grade 1 or Grade 2, regardless of relationship to study drug: Continue study product and manage participant according to standard of care practice at the site.
- **Grade 3 assessed as not related:** Continue study product and re-evaluate participant at least weekly until improvement to Grade 2 or lower. If improvement to Grade 2 or lower cannot be documented in 2 weeks, consult the CMC.
- **Grade 3 assessed as related:** Temporarily hold study product use, notify the CMC, and reevaluate the participant at least weekly until improvement to Grade 2 or lower. If within 2 weeks the adverse event has improved to Grade 2 or lower, study product may be resumed. Consult the CMC if improvement to Grade 2 or lower cannot be documented within 2 weeks
  - o If study product use is resumed and the same Grade 3 adverse event deemed related to study product, recurs at any time, the IoR/designee must temporarily hold study product and consult the CMC for further guidance on continuing the temporary hold or progressing to permanent discontinuation of the study product.
- **Grade 4 regardless of relationship to study drug:** Temporarily hold study product, re-evaluate the participant as soon as possible or within 2 business days, and consult the CMC. Continue the temporary product hold until a recommendation is obtained from the CMC.

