#### 8.1.5 Lipase Elevations and Pancreatitis

Participants with asymptomatic elevations in lipase should be managed as follows, regardless of relationship to study drug:

- **Grade 1 or 2:** Continue study product, and be followed for development of symptoms (i.e., pancreatitis) according to standard of care practice at the site.
- **Grade 3 or higher:** Temporarily hold study product, and repeat testing on a newly obtained sample within 2 weeks. If the repeat test result is Grade 2 or lower, resume study product. If upon resuming study product lipase elevation is Grade 3 or higher, permanently discontinue study product. If the repeat test result is Grade 3 or higher, and in the absence of other diagnoses, permanently discontinue study product.

Participants with a confirmed diagnosis of clinical pancreatitis (i.e., symptomatic elevations in lipase) should be managed as follows:

- Grade 2 or higher assessed as not related: Temporarily hold study product, notify the CMC within 48 hours, and re-evaluate the participant weekly until complete resolution (i.e., return to baseline). Upon returning to baseline, resume study product and re-evaluate the participant every 2 weeks for at least 6 weeks. If after resuming study product, any elevation of lipase of Grade 2 or higher, or any recurrence of symptoms, then permanently discontinue study product.
- **Grade 2 or higher assessed as related:** Permanently discontinue study product, and notify the CMC.

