## 8.4 Deferring Study Product and Criteria for Temporary Hold of Study Product

At each study product administration time point, the site investigator or designee must confirm participant eligibility to receive study product (see Section 6.8). Study product administration must be deferred consistent with the guidance provided in Section 8.4.

For any other significant medical condition that, in the opinion of the investigator, would make it unsafe to administer study product or make it difficult to assess for subsequent study drug related adverse events, if present on the scheduled day of study product administration, administration must be deferred, and the CMC should be consulted on next steps and continued study product management.

For all temporary holds, both study products should be held, and the CMC should be consulted as soon as possible and within 48 hours; the CMC may recommend resuming a (non-study provided) cART regimen in these situations. For participants resuming a cART regimen for the duration of a temporary study product hold, site staff should provide the participant and the participant's parent or guardian with referrals to non-study sources of treatment for the participant, as applicable. See the IMPAACT 2036 MOP for operational consideration and guidance.

Study product will be temporarily held from a participant for any of the following reasons:

- Study product management per Sections 8.1 through 8.4.
- Report of use of prohibited concomitant medications (See Section 5.7). Study product use may
  resume upon consultation with the CMC and when the participant reports that he/she is no
  longer taking the prohibited medication, provided other reasons for temporary study product
  hold/permanent discontinuation do not apply. The CMC should be consulted in all cases of a
  participant reporting taking a prohibited concomitant medication during the course of the study.
- The participant is unable or unwilling to comply with required study procedures, such as protocol-required laboratory assessments or injectable study product visits, or otherwise might be put at undue risk to their safety and well-being by continuing study product use, according to the judgment of the site investigator. The site investigator must consult the CMC on all temporary study product holds instituted for this reason, for further guidance on resuming study product use, continuing the temporary hold, or progressing to permanent discontinuation.

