## 8.5 Criteria for Premature Permanent Discontinuation of Study Product

See Section 6.6 for guidance regarding participant management in the event of early termination or withdrawal from study participation. Administration of study product will be permanently discontinued in the following circumstances:

- Participant intention to discontinue study product or study follow-up
- During the oral lead-in phase, sustained non-adherence to oral regimen that, in the opinion of the investigator and in consultation with the CMC, warrants early study product discontinuation.
- Sustained non-adherence to injection visit schedule that, in the opinion of the investigator and in consultation with the CMC, warrants early study product discontinuation (per IoR discretion, a temporary product hold may be initially implemented; see Section 8.5).
- The participant requires treatment with prohibited medications (see Section 5.7).
- During the oral lead-in phase, confirmed pregnancy; see Section 8.4 for product management during injectable phase in the context of a positive pregnancy test.

- Participants of childbearing potential who are engaging in sexual activity that could lead to
  pregnancy refuse use of an effective contraceptive method without an intention to
  resume/initiate.
- The participant experiences an adverse event that requires discontinuation as defined in Section 8.1.
- Virologic failure as described in Section 8.3.
- The site investigator determines that further administration of study product would be detrimental to the participant's health or well-being.
- New data become available that indicate study products should be discontinued as determined by the CMC.

Participants who permanently discontinue study product should resume (non-study provided) cART as follows:

- Cohort 1 and Cohort 2a participants during the oral lead-in phase: as soon as possible and within 4 weeks of their last oral study product use.
- All participants during injectable phase and on a Q4W dosing regimen: within 4 weeks of their last study product injection.
- All participants during injectable phase and on a Q8W dosing regimen: at 8 weeks ( $\pm 7$  days) after their last study product injections.

Participants who permanently discontinue oral study product will be instructed to return all oral study products to the site clinic as soon as possible.

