See Section 6.6 for the specified participants who will be followed per the LSFU visit schedule upon permanent discontinuation of study product.

Participants who prematurely permanently discontinue study product during the oral lead-in phase for reasons other than pregnancy or are otherwise not eligible to progress to the injection phase will be terminated from the study. These participants should complete an Early Termination visit 28 days after last oral study product use; see Section 8.6 below for additional guidance in the event of termination from the study.

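### Sections 8.1.1, 8.1.4 and 8.1.5 let oral dosing resume or continue in the lead-in after a related Grade 3 event, although 4.4.2 already bars that child from injection

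*Protocol*

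**What the plan says.** **Management of the event.** Section 8.1.1 orders a hold for a Grade 3 event assessed as related, and then: "If within 2 weeks the adverse event has improved to Grade 2 or lower, study product may be resumed". Section 8.1.5 covers asymptomatic lipase of Grade 3 or higher, whether or not it is related. Product is held and the test repeated within two weeks, and then: "If the repeat test result is Grade 2 or lower, resume study product". Section 8.1.4 continues product after a Grade 3 CK while the test is repeated within 14 days. None of the three distinguishes the oral lead-in from the injection phase.

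**What counts as an event.** The adverse-event list in Section 7.2 includes "Grade 3 or higher laboratory-only adverse events", so an isolated lipase or CK result can qualify.

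**Eligibility for injection.** Section 4.4.2 excludes a child from Step 2 on "Occurrence of any grade 3 or higher adverse event assessed as related to study product during Step 1". It contains no exception for recovery.

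**Consequence of ineligibility.** Section 6.3.3, which describes the Week 4a visit, says that ineligible children: "they will permanently discontinue oral study product use and complete an Early Termination visit 28 days after their last oral study product dose". Section 3.1 also has them exit. Section 8.5 says that children who stop early in the lead-in, or who "are otherwise not eligible to progress to the injection phase will be terminated from the study".

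**The concern.** Section 1.3.1 gives one purpose of the lead-in as finding acute toxicity before a depot injection that cannot be removed. Once a related Grade 3 event has occurred and stays attributed to study product, that purpose has been met for that child, and the route to injection is closed. Any further oral dose exposes the child again to the suspected drugs. The return is small: a little extra lead-in safety data and perhaps some PK.

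The concern is that the adverse-event section, which a site will open when the event happens, points the other way from the eligibility section. What is at stake is avoidable exposure of individual children aged 2 to under 12, rather than any statistical property of the trial.

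**Working it through.** The plan states no figure on this point, so the check is mainly a comparison of texts.

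1. **When the bar arises.** 4.4.2 turns on occurrence. If the event is found at the Week 2 visit and assessed as related, the child is ineligible from then on. Improvement does not undo this.
2. **What 8.1 then tells the site.** 8.1.1 permits a restart. 8.1.5 directs one. 8.1.4 does not interrupt dosing at all. A site that follows 8.1.5 to the letter for a related lipase event doses a child whom 4.4.2 has barred.
3. **When the stop operates.** 6.3.3 rests the eligibility decision on data gathered through Week 4a. Sections 8.1.1, 8.1.4 and 8.1.5 do not refer to 4.4.2 or 6.3.3. The criteria listed in 8.5 do not name Step 2 ineligibility or a related Grade 3 event as such.
4. **Whether the silence is deliberate.** Elsewhere Section 8 does write lead-in rules. Confirmed pregnancy (8.2) and confirmed virologic failure (8.3) in the lead-in lead to discontinuation or termination. A related rash before Week 4b requires consultation with the Clinical Management Committee (CMC) before injection (8.1.9). The gap therefore looks like drafting.

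**Possible length of re-dosing.** Appendix II puts Week 2 at Day 14 with a window of -7/+6 days (Day 7 to 20). It puts Week 4a at Day 28 with a window of -7/+10 days (Day 21 to 28 + 10 = 38). Days of re-dosing = day of Week 4a minus day of resumption.

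| Found | Resumed | Week 4a on Day 28 | Week 4a on Day 38 |
|---|---|---|---|
| Day 14 | Day 21 | 28 - 21 = 7 | 38 - 21 = 17 |
| Day 14 | Day 28 | 28 - 28 = 0 | 38 - 28 = 10 |
| Day 7 | Day 14 | 28 - 14 = 14 | 38 - 14 = 24 |

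Detection and resumption days are assumptions. The rows are examples and do not bound the duration. The upper figures also suppose that nobody applies 4.4.2 before the visit.

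**How many children.** The protocol gives no Step 1 rate of related Grade 3 events. At an assumed 1-2%, the expected number is 50 x 0.01 = 0.5 to 50 x 0.02 = 1.0 at N=50, and 70 x 0.01 = 0.7 to 70 x 0.02 = 1.4 at N=70. The chance of at least one is 1 - (1 - p)^N: 0.395 to 0.636 at N=50 and 0.505 to 0.757 at N=70, in line with Table 8 (0.39, 0.64, 0.51, 0.76). These figures concern the index event only. Re-dosing needs several further conditions for which the protocol gives no probability.

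**Effect on the analysis.** The outcomes in 9.2 are proportions of children. The index event already makes the child a drug-related safety failure, and under 3.2 it already makes a Cohort 1 child evaluable and dose-evaluable. The oral PK measures in 10.2.1 are all at Week 2, and 6.6.2 takes no PK sample when a child leaves during Step 1. Re-dosing after Week 2 therefore adds little.

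**The case against.** The strongest reply is that the stop rule exists. 6.3.3 is conditioned on ineligibility, the closing rule in 8.5 carries no visit date, and 8.1.1 is only permissive. A specific mandatory rule should prevail over a general permission, which would leave only a missing cross-reference.

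There are also several checks. For any hold, 8.4 says "the CMC should be consulted as soon as possible and within 48 hours", and it has the investigator confirm at each administration that the child may receive product. Section 6.9 requires a review before oral product is dispensed, and 5.6 has held children return their supply. Under 8.5 the investigator can stop on judging that "further administration of study product would be detrimental to the" child's health or well-being. Under 9.5.3 the CMC can discuss attribution with the site. Many related Grade 3 events are permanent stops already: allergic reaction, rash, pancreatitis and QTc prolongation.

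Most of this stands, and it makes re-dosing unlikely. It does not remove the conflict. Reading the specific rule over the general one works for 8.1.1, but 8.1.5 is itself specific and directive. In the 8.1.4 case there is no hold, so the 48-hour consultation is not triggered. Consultation is also not a bar on restarting.

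A reader might go further and infer that the protocol has no stop rule, or that it requires re-dosing in general. Neither is supported: 3.1, 6.3.3 and 8.5 do stop the child, and only 8.1.5 directs resumption. That direction is correct for unrelated lipase elevations.

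**Conclusion.** The sections conflict, and a child already barred from injection could be given oral study product until Week 4a. This holds only while the event remains assessed as related, and only for event types that 8.1 does not already make a permanent stop. It is unlikely in practice and few children would be affected. No estimate, sample size or index-event safety count changes.

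Two stronger readings of the numbers should be resisted. The 39-76% span is the chance of at least one index event at an assumed rate, not the chance that a child is re-dosed. The 0 to 17 days obtained for an event found on Day 14 is not a general range; it follows from the chosen detection and resumption days. The point is worth correcting because it concerns avoidable exposure of children and costs almost nothing.

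**What to change.** Add at the opening of Section 8.1, stated to override 8.1.1 to 8.1.11:

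*In Step 1 of Cohorts 1 and 2a, any Grade 3 or higher adverse event that is confirmed (where repeat testing is specified) and remains assessed as related to study product after CMC consultation makes the participant ineligible for Step 2 (Section 4.4.2); study product is permanently discontinued without resumption and Section 6.3.3 applies.*

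List the same criterion in 8.5. Placing it at the head of 8.1 reaches 8.1.4 as well as 8.1.1 and 8.1.5. The condition on confirmation and CMC consultation keeps room for a spurious result or a revised attribution.

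The cost is one sentence and one list item. The downside is small: the child loses the option of rechallenge, and the study loses a little remaining lead-in safety or PK data from that child.

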#### 8.1.2 Injection Site Reactions (ISRs)

An ISR is defined as an adverse event which, in the opinion of the IoR or designee, results in pain, tenderness, erythema, redness, induration or swelling, or pruritis. ISRs should be assessed and reported per the Site Reactions to Injections and Infusions section of the DAIDS toxicity tables.

Participants with ISRs should be managed as follows, regardless of relationship to study drug:

- **Grade 1 or Grade 2:** Continue study product, and manage the participant symptomatically (e.g., cold/warm compress, acetaminophen, ibuprofen).
- Grade 3 or 4: Consult the CMC to determine etiology and study product management.

Please see the IMPAACT 2036 MOP for more details related to ISRs.

## 8.1.3 Suspected IM Maladministration and/or Post-Injection Reaction

In the event that a participant experiences a serious post-injection reaction or IM maladministration is suspected at any time (e.g., suspected under or overdose or inadvertent IV dosing), the investigator should request that the participant stay onsite for approximately 2-3 hours post-dose for safety monitoring. An ECG or any other supportive testing may be obtained at the discretion of the investigator. Additionally, PK samples should be drawn approximately 2 hours post-dosing for

evaluation of CAB and RPV plasma concentrations. The CMC should be notified immediately and no later than 24 hours after a suspected maladministration event. Additional safety labs may be requested by the CMC or collected per investigator discretion.

## 8.1.4 Creatine Kinase (CK/CPK) Elevation

All participants with elevated CK results from baseline should be assessed for physical activity or exercise preceding the CK sample collection. Participants should abstain from exercise for more than 24 hours and be well hydrated prior to any repeat sample collection.

- **Grade 1 or 2:** Continue study product.
- **Grade 3:** Continue study product and repeat testing from a new sample within 14 days. If the repeat test result is Grade 3 or higher, consult the CMC within 48 hours.
- Grade 4, with no signs/symptoms of rhabdomyolysis: Continue study product and repeat testing from a new sample within 7 days, and after the participant has abstained from exercise for >24 hours. If the repeat test result is Grade 2 or lower, manage per grade. If the repeat test result is Grade 3 or higher, consult the CMC within 48 hours for further guidance on study product and participant management.
- **Grade 4, with signs/symptoms of rhabdomyolysis:** For Grade 4 CK elevations that are in the opinion of the IoR associated with signs/symptoms of rhabdomyolysis (such as myalgias, muscle pain, dark urine, or clinically significant changes in creatinine clearance or eGFR), temporarily hold study product, repeat testing from a new sample within 7 days, and consult the CMC within 48 hours for further guidance on study product and participant management.

#### 8.1.5 Lipase Elevations and Pancreatitis

Participants with asymptomatic elevations in lipase should be managed as follows, regardless of relationship to study drug:

- **Grade 1 or 2:** Continue study product, and be followed for development of symptoms (i.e., pancreatitis) according to standard of care practice at the site.
- **Grade 3 or higher:** Temporarily hold study product, and repeat testing on a newly obtained sample within 2 weeks. If the repeat test result is Grade 2 or lower, resume study product. If upon resuming study product lipase elevation is Grade 3 or higher, permanently discontinue study product. If the repeat test result is Grade 3 or higher, and in the absence of other diagnoses, permanently discontinue study product.

Participants with a confirmed diagnosis of clinical pancreatitis (i.e., symptomatic elevations in lipase) should be managed as follows:

- Grade 2 or higher assessed as not related: Temporarily hold study product, notify the CMC within 48 hours, and re-evaluate the participant weekly until complete resolution (i.e., return to baseline). Upon returning to baseline, resume study product and re-evaluate the participant every 2 weeks for at least 6 weeks. If after resuming study product, any elevation of lipase of Grade 2 or higher, or any recurrence of symptoms, then permanently discontinue study product.
- **Grade 2 or higher assessed as related:** Permanently discontinue study product, and notify the CMC.

